5 A: To prove the feasibility of centralized remote monitoring of continuous EEG monitoring in the NICU via the internet, thereby developing infrastructure vital to further neonatal seizure research.

Hypothesis: Remote video continuous EEG monitoring is feasible, cost effective, and will allow rapid treatment decisions necessary for future trials of anticonvulsant efficacy in neonates.

5 B: To test the sensitivity and specificity of a promising neonatal seizure detection algorithm in comparison with readings of each record by 2 encephalographers skilled in neonatal EEG analysis.

Hypothesis: A novel seizure detection algorithm will have a high sensitivity and low false positive detection rate, which will allow use in future clinical trials of neonatal seizure management.

6. BACKGROUND AND SIGNIFICANCE:

There are no FDA approved treatments for neonatal seizures (seizures occurring in the first 28 days of life). More effective and less toxic treatments are urgently required. While appropriately holding orphan drug status, neonatal seizures are a common problem within the field of child neurology and cause significant morbidity. Current standard of care treatments Phenobarbital and phenytoin are unsatisfactory¹, each agent is effective in less than 50% of subjects, and both have significant acute and chronic side effects. In animal studies these agents cause accelerated neuronal apoptosis in the neonatal brain. Better treatments could limit brain damage and improve neurodevelopmental outcomes in this high risk population. Levetiracetam (LEV) has great potential as a treatment for neonatal seizures, but is not approved for use in children less than 2 years of age. Given the orphan nature of neonatal seizures and the fact that LEV is out of patent, the pharmaceutical company that manufactures LEV will not seek market approval in this unprofitable age group. LEV has established efficacy and an excellent safety profile in older patients. In animal models this agent does not cause neuronal apoptosis and is neuroprotective. However, the efficacy of LEV has not been systematically studied in neonates and cannot be assumed. Drugs that are effective in terminating seizures in adults may be less effective and have more toxicity in neonates. This study aims to obtain essential data regarding the efficacy and safety of LEV in this vulnerable and under researched population.

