Feasibility data: We will record the times of the following events: subject admission to NICU, contact of study staff by treating physicians, subject enrolment, initiation of EEG monitoring, first recognized seizure, and time of study drug administration. Record will be made of whether seizure is first identified by Corticare staff or by onsite study investigator. Record will be systematically collected from each monitored subject of any difficulties with functioning of the remote continuous monitoring infrastructure. All data will be referenced to date/time of birth so that precise age in hours can be determined for age at enrolment, timing of seizures, administration of study drug, and administration of other treatments given to treat seizures.

Safety data: Continuous monitoring of vital signs will occur as part of routine neonatal intensive care. Vital signs will be recorded at baseline, and at 15 minutes after each drug infusion commences. Documentation of presence or absence of adverse event occurring during each treatment phase will be made. Blood tests of haematological indices, electrolytes, glucose, renal function and liver enzymes will be tested and recorded at baseline, at 24 hours and at 48 hours as part of safety and adverse events monitoring.

Pharmacokinetic data: For subjects at the 3 San Diego sites serum LEV levels will be drawn at baseline, 1 hour after starting the treatment, at 24 and 48 hours.

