EEG data monitoring and automated seizure detection: Gold standard 9 channel neonatal montage continuous video-EEG data will be collected for 24 to 48 hours after study drug administration with the length of monitoring time determined by the Principal Investigator for each site. There may be infants who, after 24 hours of remaining seizure-free, are appropriate for discontinuation of monitoring which also may enable them to be safely discharged home. Babies undergoing hypothermia for hypoxic ischemic encephalopathy will have EEG monitoring data captured for 24 hours post start of rewarming as this is a high risk time for seizures. Each site will use available video EEG equipment with Persyst software installed. A research dedicated Cadwell video EEG system is requested under this grant for each site. Following recruitment to monitoring, each site will have their study investigator monitoring the EEG in real time, per the study algorithm. Corticare technicians will provide continuous EEG monitoring by remote access to the acquisition station. If Corticare or the real time onsite observer detects seizure activity the site investigator or local encephalographer will immediately be contacted to review the tracing. Neonatal EEG data obtained from conventional digital EEG machines based at the study sites will be monitored in near- real time using Persyst Insight software running

on the acquisition stations via the site's local area network or remotely via secure Internet access utilizing Citrix server, Microsoft Remote Desktop, or similar institutional remote access capabilities. The EEG data will be continuously analyzed in near- real time using Persyst MagicMarker in order to produce and display EEG data trend graphs. The graphical EEG trends will include Rhythmic Run Detection and Display, amplitude integrated EEG, FFT spectrograms, asymmetry spectrograms, and other trends useful in the rapid recognition of seizures. Following completion of the local study on each subject the full video EEG (totalling 5 Gigabytes of data/ 24 hours) will be archived on the UCSD server for analysis by the encephalographers. Data transfer will be achieved where possible by encrypted internet connections. Alternatively the studies will be mailed on memory sticks or DVDs. Archived video continuous EEG data will be available for trend analysis and seizure detection comparison with the duplicate formal encephalographers reading of the 48 hours of tracing.

Add on Study:

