Feasibility will be measured by accuracy and speed of notification of electrographic seizures. We will report the standard metrics of sensitivity and specificity. If Corticare reports a seizure rejected by the study investigator, this will be recorded as a false positive. Conversely seizures recorded by the neurophysiologist but missed by Corticare will be false negatives, and we will determine the rate of false positives and false negative seizure reports by Corticare technologists. We will calculate the specificity and sensitivity of Corticare seizure reporting. For speed of reporting, we will measure the time lapse between the occurrence of seizure and site study investigator notification and the lapse between occurrence of seizure and study drug administration. Descriptive report of technical difficulties experienced with the remote centralized EEG review system will be made.

Analysis plan for Aim 5 B. Analysis of performance of the automated seizure detection algorithm

In addition to standard visual EEG review by the study's electroencephalographers, the early detection of seizures will be assisted by automated seizure detection notifications generated by the computerized algorithm. These notifications, and images of their associated EEG tracing and graphical trends, can be automatically broadcast via email to specifically designated study personnel for verification of the nature of the detected event. The performance of the seizure detection algorithm will be assessed by comparing its output to the final EEG markings of two neonatal electroencephalographers. The following seizure detection algorithm performance parameters will be calculated: overall seizure detection sensitivity, false positive rate, and seizure-affected patient detection rate (the percentage of patients with seizures in whom at least one seizure is correctly identified).

9. HUMAN SUBJECTS:

The trial will be a Phase II trial to test the efficacy, pharmacokinetic and safety of intravenous Levetiracetam (LEV) as first line treatment for neonatal seizures with greater than minimal risk.

Human Subjects Involvement and Characteristics

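### Aim 5A's seizure-to-drug lapse, and its notification lapse unless limited to Corticare's reports, reflects the faster of two readers and cannot alone show that remote monitoring is rapid

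*Protocol*

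**What the plan says.** The hypothesis for Aim 5A (Protocol section 5) is: "Remote video continuous EEG monitoring is feasible, cost effective, and will allow rapid treatment decisions necessary for future trials".

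The Analysis Plan for Aim 5 A (Protocol section 8) states: "Feasibility will be measured by accuracy and speed of notification of electrographic seizures". The two components are handled differently.

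- **Accuracy** is specific to the remote service: sensitivity, specificity, false positives and false negatives of Corticare's reports.
- **Speed** is given as "we will measure the time lapse between the occurrence of seizure and site study investigator notification and the lapse between occurrence of seizure", with study drug administration as the second end point. No denominator is stated, and there is no split by who detected the seizure.

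The paragraph on EEG monitoring in section 8 describes parallel reading: "each site will have their study investigator monitoring the EEG in real time, per the study algorithm". On the trigger it says: "If Corticare or the real time onsite observer detects seizure activity the site investigator or local encephalographer will immediately be contacted". The Analysis plan for Aim 5 B adds a third channel: "the early detection of seizures will be assisted by automated seizure detection notifications generated by the computerized algorithm".

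The Feasibility data paragraph in section 8 says: "Record will be made of whether seizure is first identified by Corticare staff or by onsite study investigator". The Aim 5A analysis does not use that item. The event times listed there include the first recognized seizure and study drug administration, but no time at which Corticare or the investigator was notified of a seizure. No cost or staff-time item is listed.

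The note closing SAP section 3.2 takes Aims 5A and 5B out of the primary analysis because monitoring changed during the study. SAP section 7 contains no analysis for Aim 5A.

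**The concern.** The claim to be supported is about the remote service: that it allows decisions to be made quickly. A time that stops when either of two readers raises the alarm measures the combined system. If the onsite reader is usually quicker, the lapse will be short whatever the remote reader does.

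This matters because Protocol section 6 motivates central remote review by the shortage of neurologists able to read EEG around the clock at each hospital. A speed obtained with an onsite reader in place does not carry over to a setting without one. Sensitivity does not fill the gap: a remote reader who reports every seizure late would score well on sensitivity while the combined lapse looked fast.

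The hypothesis also claims cost effectiveness, and nothing listed for collection bears on it.

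**Working it through.** **No stated figure to reproduce.** The documents give no detection time, target lapse, success threshold or sample size for Aim 5A. The check is one of logic, followed by an illustration on assumed lags.

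**Step 1: which quantity each lapse measures.**

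| Lapse | Stops when | Depends on |
|---|---|---|
| Seizure to study drug | Drug is given after a confirmed seizure | Whichever channel raised the seizure first |
| Seizure to investigator notification | Investigator is contacted | Either reader under the EEG monitoring paragraph; Corticare only, if speed of reporting is taken to continue the preceding sentence on Corticare |

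Where the onsite reader is the site investigator, the notification lapse is not clearly defined for a seizure found onsite.

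**Step 2: illustration (all lags assumed).** Let the onsite and remote lags be independent exponentials with medians m_O and m_R minutes. The observed lapse is the smaller of the two.

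- Median of the observed lapse = m_O × m_R / (m_O + m_R)
- Share first found remotely = m_O / (m_O + m_R)

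| m_O | m_R | Observed median | Remote first |
|---|---|---|---|
| 5 | never detects | 5.0 | 0% |
| 5 | 60 | 300/65 = 4.6 | 5/65 = 8% |
| 5 | 15 | 75/20 = 3.75 | 5/20 = 25% |
| 5 | 5 | 25/10 = 2.5 | 5/10 = 50% |
| 30 | 5 | 150/35 = 4.3 | 30/35 = 86% |
| 30 | never detects | 30 | 0% |

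With a quick onsite reader, the observed median moves only from 3.75 to 5.0 as the remote reader goes from a 15-minute median to never detecting. With a slow onsite reader it moves from 4.3 to 30.

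**Step 3: imperfect detection (simulated, also assumed).** Onsite detection probability was set at 95%, and remote detection probability at 0, 30, 79 and 100% in turn.

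- Onsite median 3, remote median 30: observed medians 3.0, 3.0, 2.9 and 2.9. The remote reader's own median is about 30 wherever it detects at all.
- Onsite median 10, remote median 5: observed medians 10.0, 7.0, 4.1 and 3.4.

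The observed lapse can thus be almost blind to remote performance or strongly dependent on it, and the lapse alone does not show which case applies.

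**Step 4: what a split by first identifier can show.** Seizures found first by Corticare are those where it beat the onsite reader. In the model of step 2, with rates λ_R = ln 2/m_R and λ_O = ln 2/m_O, P(remote lag > t | remote first) = exp(−(λ_R + λ_O)t), which is the distribution of the combined lapse. With medians of 5 and 15, the Corticare-first median is 3.75, not 15. The split must therefore be read with the proportion first found by Corticare (25% here), and the subset described as selected.

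**The case against.** Several points on the other side are sound.

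- **The notification lapse may be Corticare-only.** The section heading concerns the remote system, and the sentence just before the speed measures is about Corticare's reporting. That reading is plausible, but the text does not state it. It does not help the drug lapse.
- **No denominator is given.** A reader might infer that both lapses are computed over all seizures. The text does not say so. The listed times, with first recognized seizure and drug administration, suggest one drug lapse per treated infant.
- **Accuracy is reported too.** A reader might infer that Aim 5A could succeed even if remote monitoring contributed nothing. The documents do not support that: feasibility is judged on accuracy as well as speed, and Corticare's own sensitivity and false negatives would expose a useless remote reader. What sensitivity leaves open is timeliness.
- **The size is assumed.** Lags chosen with a quick onsite reader make the lapse look insensitive; reversing them does the opposite. The staffing shortage described in Protocol section 6 means a consistently faster onsite reader is not a safe default.
- **The SAP has set the aim aside.** It places Aim 5A outside the primary analysis and does not say what changed in monitoring, so parallel reading may not have continued as described. However, SAP section 5.2 still refers to planned analyses identified in the research plan, and the Protocol text is the only analysis given for this aim.

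**Conclusion.** The point holds in a limited form. The seizure-to-drug lapse follows the faster of the remote and onsite readers, as does the notification lapse unless it is confined to Corticare's reports. Neither lapse alone supports the claim that remote monitoring allows rapid treatment decisions. This rests on the either-reader trigger and the absence of any split in the Aim 5A analysis, not on the illustrative lags. The size cannot be stated from the documents.

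The cost-effectiveness claim has no supporting data item, which is a separate and simpler fault of wording.

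The importance is minor. Aim 5A is descriptive, has no test or threshold, and lies outside the SAP's primary analysis. Nothing here touches the efficacy or safety conclusions.

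**What to change.** In any report of Aim 5A:

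1. State what the monitoring arrangement was after the changes noted in the SAP, and whether the notification lapse covers Corticare's reports only.
2. Present both lapses split by first identifier, which is already recorded, with the proportion of seizures first identified by Corticare.
3. Base any statement on remote speed on Corticare-first seizures, and say that these are a selected subset which can flatter the remote reader.
4. Where Corticare's own notification times exist, report them for every confirmed seizure, counting misses as not notified. This is preferable to censoring the remote time at onsite identification: a conspicuous seizure is likely to be quick for both readers, so that censoring would probably be informative.
5. Remove cost effectiveness from the hypothesis.

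Items 1, 2, 3 and 5 need wording and a field already collected. Item 4 depends on timestamps that the feasibility list does not name, so the sponsor should first confirm that they exist. The downside is that the remote speed estimate will be less precise and may look less favourable.

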Data that will be collected specifically for the purposes of this trial will include clinical data regarding the subjects' medical history and hospital course including clinical characteristics such as weight, medications administered, blood pressure measurements, and fluid input/output. Most clinical data will be obtained from the subjects' medical records, but there may be some data obtained by interviewing the parent(s).

Much of the laboratory data that will be recorded in the database will be laboratory data obtained in newborns as part of standard clinical care of newborns with seizures, such as serum blood gas measurements, serum electrolytes, levels of AEDs administered and liver function tests. Some laboratory tests such as albumin and serum bicarbonate may not be collected at both time points for standard care for some subjects and thus will be obtained for purposes of the trial. Serum LEV levels will be collected only for purposes of this trial.

EEG data will be read and used for clinical purposes at each site with the assistance of the remote centralized continuous monitoring system. For the purposes of the study itself EEG data collected at each site will be de-identified before analysis by the study neurophysiologists who will be blinded to the subjects' group assignment or demographic information.

Study staff at each site will have access to individually identifiable information about newborns enrolled at that site. Data will be collected by each site's study investigators and the research coordinator and recorded onto case report forms (CRFs) by the research coordinator, and data from the CRFs will subsequently be entered into the database by the research coordinator. The CRFs and the electronic database will only have de-identified information to preserve confidentiality of patients' protected health information. Files that link the study identification number for each subject to the subject's personal information (such as name, medical

record number, parents' names) will be kept at each site and accessible only by the site PI and research coordinator.

10. RECRUITMENT AND SCREENING:

300 subjects will be recruited in total from the 5 NICU's over 4 years. A higher than anticipated screening to treatment ratio of approximately 3:1 monitored to treated neonates has occurred in the initial 85 neonates recruited to this study. The originally anticipated 2:1 EEG monitoring: treatment ratio is likely lower due to the beneficial effects of hypothermia treatment many neonates receive as a usual standard of care. Hypothermia treatment may be reducing the incidence of seizures in this population. This change in ratio may also be a reflection of a benefit of this study in that behavior in a few neonates which may have previously been clinically judged to reflect seizure activity, because of continuous EEG monitoring viewed by EEG technicians in this study also reviewed by a neurologist, have been correctly diagnosed as myoclonic jerks rather than seizures. This has thereby prevented some neonates from receiving medication for seizure treatment because their behavior is not confirmed by their EEG as seizure activity. For these reasons an increased number of total subjects will be needed in this study in order for 100 subjects to be treated.

Inclusion Criteria:

Term newborns admitted to the UCSD, Children's Hospital and Research Center Oakland, Auckland Hospital, Rady Children's Hospital or Sharp Mary Birch NICUs with seizures or at risk for seizures:

- Term infants (gestational age greater than or equal to 36 weeks)
- Postnatal age < 14 days.
- Serum creatinine equal to or less than 1.6 mg/dL at time of enrollment
- Are still experiencing either clinical or electroencephalographic seizures or are at risk for neonatal seizures.
- For whom parental consent to participate in the study is obtained.

Exclusion criteria:

- Biochemical abnormality – hypoglycemia, hypocalcemia- that when treated result in seizure cessation.
- Severe hypoxic ischemic injury likely to result in imminent death
- Infants with a birth weight less than 2200 g would be excluded the study. This is the new recommended 10th percentile for 36 weeks gestation. The blood drawn at any one time will be <3 mls/kg which remains within the NIH guidelines for pediatric blood draws.

Patients of all ethnic groups will be included in the study. Based on the patient population our group treats, most patients will be European or Hispanic. Both male and female infants will be recruited to the study.

The only significant exclusions that will be made in recruitment and enrollment will be the exclusion of infants who are judged by the attending neonatologist to be so critically ill that death is imminent and benefit from neonatal intensive care is very unlikely. No rule-based criteria, (using lab or clinical parameters) adequately capture the complete nature of this clinical assessment. In general any child receiving active treatment with head cooling will not be excluded. Mechanical ventilation and/ or the use of inotropic agents to support blood pressure will not be exclusion criteria.

These patients will be a very sick population, reflecting the underlying etiology of the seizures as well as the physiologic effects of seizures per se. Approximately 50% of neonatal seizures are caused by hypoxic ischemic encephalopathy, (HIE). These infants have sustained global hypoxic ischemic injury with consequent renal, hepatic, gastrointestinal, respiratory and cardiac sequelae. Other common etiologies of

neonatal seizures include intracranial hemorrhage, infection and developmental defects, which may also be associated with impaired function of other organs. Therefore seizures are frequently associated with high mortality and morbidity. In studies of term infants with neonatal seizures, it has generally been found that between 20 to 30% died, 20 to 30% developed post-neonatal epilepsy and between 20 and 40% developed cerebral palsy^{1,2}.

Commonly, it is expected that a new drug or drug formulation would be studied extensively in healthy adult populations prior to its use in studies in vulnerable newborns. The basic assumption underlying this common practice is that standard management is adequate. This is not the case in the treatment of neonatal seizures. Agents that have good efficacy and safety in the mature brain, (Phenytoin and Phenobarbital) are much less effective and have increased toxicity in the immature brain. The dire need for better treatments for neonatal seizures, combined with the existing data that suggest that this new agent may well be safer than traditional agents and that it may also have good efficacy is justification for studying the drug in this population.

Infants admitted to the 5 participating NICU's will be recruited in 3 separate situations:

- A. Infants with HIE identified prospectively as being at high risk for developing seizures,
- B. Infants admitted to NICU with pathologies other than HIE that also place the infant of high risk to develop seizures.
- C. Infants with seizures as first indication of illness, transferred to the NICU for treatment. Initially etiology may not be clear but may include infection, stroke, hemorrhage, brain malformation and idiopathic seizures.

Partial HIPAA waiver will need to be granted for the recruitment procedure, specifically the waiver of consent for the transfer from the clinical team to the study team of clinical information needed to determine patient eligibility for the study.

In groups A + B it will be possible to prospectively obtain consent for participation in the trial at the time when the infant is admitted to the unit. Neonatal staff (Admitting neonatal fellow or resident) will identify eligible subjects in group A or B briefly discuss the study with patients' families and obtain permission to contact study staff. Study staff will screen the patient for inclusion and exclusion criteria as listed above and obtain consent from parents for participation in the study in the event that seizures should occur

Group C:

Frequently seizures are the first indication that a neonate is unwell. These occur in the regular postnatal nursery. Once the infant is transferred to the NICU and stabilized cardiovascularly, and if seizures are ongoing and hypoglycemia and hypocalcemia have been excluded as cause for the seizure, a continuous EEG monitor will be placed, (this is not yet standard of care in the majority of NICU's in the United States but is an option available in many centers).

While the EEG leads are being placed intensive efforts will be made by neonatal and study staff at this stage to obtain parental consent for participation in the study. If consent can be obtained the patient will be enrolled in study and a randomized to a treatment arm during the EEG set up. If electrographic seizures are confirmed, IV treatment with study drug according to the protocol will commence.

11. INFORMED CONSENT:

1. The admitting resident or fellow who identifies seizures or high risk of seizures developing in the future will request the parents' permission for the study staff to approach them to discuss their possible participation.

It will be made clear to the parents that participation is voluntary and that their child will receive standard care if they do not wish to participate. Furthermore it will be made clear that the study staff is separate from the infant's own primary physician and nursing group.

2. If permission is granted the study staff will be contacted and will review the clinical details to ensure inclusion and exclusion criteria are met.

3. Study staff will approach the parent with study information to obtain consent in person.

Parents not available in person, (in situations for example where the infant has been transferred from a remote hospital), will be faxed a consent form for review and signature. Study staff will be available by phone to the parents, should they have any questions regarding the faxed consent.

If the follow-on study question is left unanswered, the study team may use an IRB approved phone script to contact the family in order to complete the question. From recent review post recruitment closure, the follow-on study question was missed in approximately 10% of the consents. A waiver of documentation will be used for contacting the families, and all responses will be documented in a separate study source document.”

12. ALTERNATIVES TO STUDY PARTICIPATION:

If parents do not wish to participate in the study they will not be coerced to do so and will be reassured that their infant will continue to receive the normal standard of care. Study staff is separate from the primary physicians and nurses involved in the infants' care, which should help to free the parents from feelings of undue pressure to participate.

13. POTENTIAL RISKS:

The potential risks to the subjects include 1) adverse drug reaction risk secondary to LEV, 2) risks of blood drawing, 3) risk that LEV is a less efficacious drug and that consequently study subject will have a longer duration of seizures before adequate treatment is given 4) risks regarding confidentiality.

Potential risks related to LEV

LEV has been used for many years as an anticonvulsant in older children and adults and has a very favorable safety profile. LEV toxicity data show a very wide safety margin, with a TD50/ED50 ratio of >148 in rodents³⁷. No deaths, organ failure or other irreversible toxicity were seen after long-term oral treatment up to doses of 1,800 mg/kg/d in the rat, 960 mg/kg/d in the mouse and 1,200 mg/kg/d in the dog.³⁸ Animal fetal toxicity data are reassuring³⁸. Data from the UK Epilepsy and pregnancy register⁶⁵ documents that no fetal malformations occurred in 39 pregnancies where levetiracetam was used as monotherapy. Where levetiracetam was used with other anticonvulsants 3 major malformations occurred in 78 pregnancies.

Clinical experience with LEV use in adults and in children has found it to be well tolerated and safe^{29, 30, 33, 39-42} including 3 recent reports of use at high dosage⁴³⁻⁴⁵. In humans 2 cases of reversible thrombocytopenia have been reported. Tan et al have reported a case in which levetiracetam was implicated as a possible cause of liver failure⁶⁶. No other significant hematological, hepatic or renal toxicities have been reported. In children and adults the most common side effects are somnolence and behavioral side effects. Glauser et al⁵⁰ report 23% of children treated with levetiracetam experienced somnolence, compared to 11% of placebo patients however this side effect rarely requires cessation of treatment. Behavioral side effects associated with treatment included agitation, anxiety, apathy, depersonalization, depression, emotional lability, hostility and hyperkinesias. A total of 37.6% of children in this study reported some behavioral side effect, compared with 18.6% of placebo patients. These behavioral abnormalities were significant enough to prompt

discontinuation of treatment or dose reduction in 10.9% of levetiracetam treated patients compared with 6.2% of placebo patients.

In our recently completed pharmacokinetic and preliminary safety study of LEV in neonates, the drug was well tolerated. Only one serious adverse event occurred in this study. One subject with a brain malformation and a high Phenobarbital level required intubation while on treatment with LEV. LEV was not thought to be causal of this event. There were a few mild adverse events identified that were possibly related to treatment with LEV: mild sedation was reported in 2 subjects. In both cases this resolved spontaneously. Feeding difficulty was documented in 3 subjects. In all cases this difficulty was probably not due to LEV treatment and in all cases feeding difficulty resolved. One subject had mild apnea and bradycardia which resolved. This was probably not related to LEV treatment. Decreased urine output occurred in 1 subject with HIE. This resolved with treatment with frusemide. All blood test abnormalities were reviewed by an independent data safety monitoring board. Mild abnormalities in blood count and serum chemistries were seen, consistent with what would have been expected in this patient population of sick neonates. No serious or consistent treatment- emergent lab abnormalities were observed.

Two recent publications of LEV use in neonates reported only sedation and irritability as side effects .

It therefore appears that levetiracetam is a very safe drug with a wide therapeutic range. However, any adverse drug reaction is possible.

Potential risks of blood drawing: blood loss and pain

Blood draws will be required in a subset of patients for measuring the pharmacokinetics of LEV. For some patients there may also be additional blood drawn for safety studies, although in most patients these laboratory tests would be obtained as standard care because of their underlying illness (i.e., systemic asphyxia).

Furthermore, additional blood tests required for the study may not require additional blood draws, because laboratory tests such as liver function tests can be run on serum drawn for other purposes, such as serum electrolytes. The required volume of each blood sample for LEV levels will be 0.5 mL. Drawing a total blood volume of 2 ml/kg (ca. 3% of blood volume) over 24 hours is considered acceptable. For a 2.2-kg term newborn, this would amount to 4.4 ml of blood/ 24 hours. This protocol requires 4 samples for LEV analysis, over 48 hours for a total volume of 2 ml. For additional blood draws of laboratory tests which may not otherwise be drawn for clinical purposes, the total volume of blood will be 2-3 ml. Thus the total amount of blood drawn for research purposes will be ≤5 ml over 48 hours. It is unlikely that this small increase in the amount of blood drawn would result in significant anemia. Most blood draws will be via indwelling vessel catheter in place as part of routine care. This will render blood sampling painless and free of any risk beyond that usually associated with the care of a critically ill newborn. Blood sampling towards the end of the 1-week treatment period may require additional venipunctures or heel stick blood draws. All efforts will be made to reduce infants discomfort by warming the heel adequately prior to blood draw, administering oral glucose during blood draw and feeding infant after blood draw.

Risk of less effective drug. There is a potential risk that LEV is a less efficacious drug than standard treatments, placing study subjects at risk of a longer duration of seizures before effective treatment is given if randomized to receive LEV. This will be minimized as described in the following section.

Potential risks regarding confidentiality. There is a potential risk for breach of confidentiality, which will be minimized by the procedures described in the following section.

14. RISK MANAGEMENT PROCEDURES:

Adequacy of Protections against Risk

Recruitment and Informed Consent

Research conducted in this project will be reviewed and approved by the appropriate Institutional Review Board (IRB) for each site. Only trained study investigators listed on the IRB protocol will obtain written informed consent using the locally approved consent form.

Recruitment procedure: Newborns will be recruited from the five neonatal intensive care units (NICUs) once the IRB protocol has been approved at all the five institutions. We will provide in-servicing to NICU staff in each unit and post flyers in the NICUs to alert neonatology staff to the study's purpose, inclusion criteria, and the pager number needed to contact the study staff regarding potential subjects. We anticipate that we will recruit subjects in two groups. The first group will be subjects in whom it can be anticipated that seizures are at high risk of occurring, for example in neonates with hypoxic ischemic encephalopathy. These subjects will be identified by the neonatology staff who will then contact the investigator on call for the research study. The neonatologist will first mention the study to the parents and then ask whether the parents will give permission for the study investigators to talk with them about the study in detail. Only parents who consent to hearing about the research study will be approached regarding enrollment of their newborn. In the second acutely presenting group, neonates present with symptoms indicative of or suggestive of seizures without prior warning. It is recognised that it will not be possible to recruit all patients in this group. Efforts to obtain consent will not be allowed to delay management. However, in many cases there will be opportunity to ethically recruit and consent subjects without delaying care. For example, in cases where clinical seizures are brief and have stopped spontaneously, and in cases where there is suspicion of seizure activity but EEG confirmation is needed before AEDs are indicated.

Consent procedure: The PI and other selected study investigators (neurology and neonatology attendings and fellows) will obtain consent. All study investigators who will be obtaining consent will receive training in how to determine eligibility of subjects and how to discuss the research study and consent process with parents of a critically ill newborn. It is anticipated that some mothers may be hospitalized at a referring hospital where the baby was born; in that case the consent form will be faxed to that hospital for the parent(s) to review. If consent is obtained in part by telephone with either or both parents, the telephone consent will be witnessed by one of the medical personnel at the NICU where the newborn is being enrolled. The child's assent will not be obtained as only newborns will be enrolled. Parents will be reassured that participation in this study is completely voluntary and that a refusal to provide consent will not affect their child's clinical care. Parents will be informed that they can ask questions of study staff at any time during the study and contact information for the study staff will be provided on the consent form. The study investigator who obtains consent will ask the parent(s) questions to determine whether they have understood the informed consent process and the requirements of the study.

Data and Safety Monitoring Plan (DSMB)

The population being studied is a very sick pediatric population. A high rate of morbidity and mortality is expected in this patient group. Therefore a DSMB will be used to monitor adverse events occurring during the trial, to try to carefully determine whether the study drug is implicated in the outcome.

The study will be conducted in compliance with the IRBs of the participating hospitals and with FDA regulations, since [name] holds an IND (#109622) from the FDA for the use of LEV to treat neonatal seizures and an Orphan Drug Designation for the treatment of neonatal seizures with levetiracetam (#10-3033).

